To complete aim 1, we will contract with Tomorrow Pictures and Emory Web Services to create the Living ACTS website and embed the current Living ACTS video. We will conduct a series of individual interviews (10 total) to gain feedback on the website from individuals meeting our participant demographic profile. Participant feedback will be used to refine and finalize the intervention website. Next, the multi-center trial will collect data from 850 AA ESRD patients who have been referred for evaluation at one of four participating transplant centers in the Southeast. The proposed methods were designed to maximize the robustness of the data while minimizing bias in study design, methodology, analysis, interpretation, and reporting. Random assignment to condition (also for Aim 2) reduces the chances of initial group differences in maturational rates, historical events, and regression artifacts.⁶² Additionally treating the two groups equivalently in terms of attention to a website with embedded video, data collection methods, and instrumentation improve internal validity by minimizing testing and instrumentation effects.⁶²

Patients will be enrolled into the study through a Zoom video call or telephone call before or after their second day of evaluation at which point they will be consented verbally and undergo baseline assessment. Next, they will be randomized to condition, access either the intervention or control website, and complete an immediate follow-up assessment. Living donor inquiries will be tracked using administrative data from the transplant centers for the subsequent 12 months. Aim 3 will be achieved through the analysis of transplant center data (for context and reach), web-site usage statistics (for fidelity), study records (for recruitment), and patient-level data (for dose received). We are intentionally not testing the effect of T-REX given its alignment with the recommendations generated by the Consensus Conference on Best Practices in Live Kidney Donation.⁶³ This study is uniquely designed to isolate the effect of the individual-level intervention within a system-level intervention to determine its added value.

C.2. Preliminary Studies

C.2.1. The RaDIANT (Reducing Disparities In Access to kidNEY Transplantation)

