Through the Powerchart system, the project coordinator will review the schedule for the transplant center of all patients who will have or had an evaluation appointment during a 7 – 10 day period before or after the scheduled appointment. The coordinator will not have a relationship or familiarity with these patients prior to screening them for eligibility. The project coordinator will also review some key patient demographics (race, sex, age, and BMI) to ensure eligibility for the study. Additionally, access to patient clinical charts will be accessed via Powerchart to confirm patient eligibility (i.e. transplant status, ESRD status, and additional eligibility criteria). The project coordinator will obtain the patient's telephone number from Powerchart to call the patient to ask the patient to participate in the study. If the patient is willing to participate, the project coordinator will obtain the patient's email address to send the appropriate Zoom video call information, appointment time and date. The patient will be scheduled for a Zoom video call no later than a week from the initial phone call. The project coordinator will also call the patient one day before the scheduled Zoom video call to confirm the appointment with the patient. If the patient does not have zoom capabilities, the coordinator will set up a video call with the patient. The coordinator will also have the option to recruit a patient in-person at the transplant clinic. Data collectors will maintain all necessary clearances and perform required trainings to gain and maintain access to electronic medical records. Project coordinators will be rigorously trained on how to recruit and screen patients for study eligibility.

Eligibility Criteria. All patients referred (from dialysis facility, chronic kidney disease clinic, or self) and scheduled for an evaluation at one of the four study sites within the study time period. Our screening process will be based on information gathered from either their referral form or electronic medical record and ensure that patients are:

- (1) AA or Black
- (2) age 18 to 70 years
- (3) have BMI < 39
- (4) are English-speaking (Language eligibility will be confirmed by project coordinator during a telephone call with the patient prior to the Zoom video call)

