Proportion of study participants who have at least one living donor inquiry by friends/family of the patient over 12 months from baseline (evaluation start). This discrete outcome has been used in prior studies⁶⁹ and is a necessary step prior to LDKT. These data are currently captured for all patients as a discrete field from electronic medical record for each potential recipient. Inquiries are defined by all centers as a telephone inquiry to the transplant center's living donor (each center has a separate telephone line for this purpose). For each study site, a data collection form that captures potential recipient ID (i.e. study participant), date of living donor inquiry, and donor inquiry ID, will be securely obtained from each transplant center following a 12 month period from enrollment. Data will be collected electronically for all study participants through a secure, HIPAA-compliant data server (QualityNet) that all 4 transplant centers have used in prior SEKT Coalition studies^{53,70}.

Secondary Outcomes. Captured in the baseline and immediate follow-up survey, which will include measures of information, motivation, and behavioral skills that we have used in past research

- a. a 25-item assessment of knowledge and understanding of donation/transplantation^{60,71}
- b. a 9-item scale asking assessing motivation to ask a family member to be a living donor⁶⁰
- c. a 10-item behavioral skills scale that measures confidence in initiating a conversation about LDKT⁶⁰
- d. a 3-item behavioral intentions scale that measures intention to discuss LDKT with family members⁷²
- e. a single-item measure of comfort in initiating conversation about LDKT⁷³
- f. several items measuring demographic characteristics (age, gender, highest level of education)

Study Size Justification & Power Calculation.

Study Size Justification. There were an estimated 3,500 ESRD patients evaluated for transplantation, and 2,180 new additions to the waiting list in the four transplant center sites in 2015. The majority (61.9%) of the waitlisted patients were AA. Thus, we will have a pool of over 1400 potential study participants over the four study sites over 1 year, which will ensure we will meet our estimated sample size of n=850 AA ESRD patients (1:1 randomization). We expect that it is possible that ~25% of patients evaluated will not be eligible for transplant and thus will not have the opportunity to have LDKT, and these patients not be considered in main outcome analyses.

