Power Calculation for Primary Endpoint. Based on preliminary data showing that the proportion of AAs with ≥ 1 living donor inquiry is 12% at baseline, we have 80% power to detect a 7% difference between the intervention and control groups, accounting for potential correlation of patients within study sites (correlation on the same subject of 0.5), with $\alpha=0.05$. We expect little attrition in this trial, since follow-up data on the number of living donor inquiries will be obtained through medical record review. Based on our prior trial,⁹ we expect >90% participation.

Statistical Analysis Plan. We will initiate the analytical process by conducting basic descriptive statistics on all variables, examining continuous variables for normality, and exploring the Cronbach's alpha for relevant scales.

- Our main analyses seek to answer the following hypothesis:

H₁: A greater proportion of participants who receive a culturally-sensitive website with embedded video (Living ACTS) will have at least one living donor inquiry over the subsequent 12 months than control participants who received standard education.

- Our secondary analyses seek to answer the following hypothesis:

H₂: Patients in the intervention (vs. control) group will have a significantly greater increase in knowledge, motivation, and self-efficacy for the behavioral skills to initiate a conversation about LDKT with family or friends from baseline to immediate follow-up

To ensure adequate balance across study arms, baseline covariates will be compared using Student *t* tests and χ^2 tests, as appropriate. Variables found to have significant differences ($p <0.05$) by study arm will be

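### The stated 80% power fits an analysis of essentially all 850 randomised patients, but the plan leaves transplant-ineligible patients out of the main analysis and the power statement makes no allowance for it

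*Combined protocol and SAP*

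**What the plan says.** All references are to the combined protocol and SAP.

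- **C.4, Study Size Justification** gives a sample of 850, randomised 1:1. It continues: "We expect that it is possible that ~25% of patients evaluated will not be eligible for transplant", and "these patients not be considered in main outcome analyses".
- **C.4, Power Calculation for Primary Endpoint**, the next paragraph, takes 12% of African American patients with at least one inquiry at baseline and says "we have 80% power to detect a 7% difference between the intervention and control groups" at alpha 0.05. It expects little attrition and participation above 90%. It also cites a correlation of 0.5, described both as between patients within a site and as on the same subject.
- **C.4, Primary Outcome** defines the endpoint as "Proportion of study participants who have at least one living donor inquiry" and equates baseline with the start of evaluation.
- **C.1, Overview** places enrolment "before or after their second day of evaluation at which point they will be consented verbally and undergo baseline assessment".
- **C.4, Patient Recruitment Methods** describes screening aimed at patients likely to be medically eligible, including a chart check ("i.e. transplant status, ESRD status, and additional eligibility criteria"). The four criteria listed under **Eligibility Criteria** are race, age, BMI and English.
- **C.4, Randomization** puts allocation directly after consent and the baseline measures.

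**The concern.** Two adjacent paragraphs appear to use different denominators. One drops a group of patients from the main outcome analyses. The other gives a power figure that, on the natural reading, uses every randomised patient.

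If part of the excluded group has already been randomised, the number analysed is below 850 and the printed 80% no longer describes the planned analysis. At stake is how a null result would be read. The plan implies a 20% chance of missing a true 7-point effect; the real chance could be materially different. A reader also cannot tell whether the primary analysis covers about 850 patients or some smaller number.

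**Working it through.** **Inputs.** Control rate 12%, difference 7 points (so 19% in the intervention arm, implied by the direction of H1), alpha 0.05, power 80%: Power Calculation. N = 850, 1:1, and the possible 25%: Study Size Justification. Two-sided testing is an assumption.

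**1. Reproducing the plan's figure.** Pooled two-proportion formula, with mean rate p̄ = (0.12 + 0.19)/2 = 0.155:

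n per arm = [1.960 × √(2p̄(1−p̄)) + 0.842 × √(p₁(1−p₁) + p₂(1−p₂))]² / d²

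- √(2 × 0.155 × 0.845) = 0.5118
- √(0.12 × 0.88 + 0.19 × 0.81) = 0.5094
- n = [(1.960 × 0.5118 + 0.842 × 0.5094)/0.07]² = 418.4, so 419 per arm and 838 in total

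The unpooled formula gives 832 and the arcsine formula 830. A continuity correction gives 894 and does not match. One-sided 0.05 needs 660, which does not match 850 either.

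Power with n per arm analysed = Φ[(0.07√n − 1.960 × 0.5118)/0.5094]. With n = 425 this is Φ(0.864) = 80.6%. The stated 80% is therefore the power of the full 850, two-sided. The 0.5 correlation is not needed to obtain it.

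**2. Can the exclusion reach randomised patients?** Patients are consented, assessed and randomised around the evaluation visits, possibly before the second evaluation day. None of the four listed criteria is a decision on transplant eligibility. The chart check may remove some ineligible patients first. The remainder can be found ineligible after allocation. The documents do not give that share.

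**3. Power if 12% and 19% hold among those kept** (two-sided 0.05):

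| Share of the 850 left out | Analysed | Power |
|---|---|---|
| 0% | 850 | 80.6% |
| 5% | 807.5 | 78.6% |
| 10% | 765 | 76.4% |
| 15% | 722.5 | 74.0% |
| 20% | 680 | 71.4% |
| 25% | 637.5 | 68.6% |
| 30% | 595 | 65.6% |

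With about 638 analysed, the difference from 12% detectable with 80% power is 8.1 points (6.9 points with 850).

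**4. Power if 12% and 19% describe all evaluated patients and 25% are left out.** In each arm, rate among those kept = (overall rate − 0.25 × rate among excluded)/0.75. The rates among excluded patients are assumptions; the documents give none.

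| Excluded, control / intervention | Kept, control / intervention | Power, about 638 analysed |
|---|---|---|
| 12% / 19% (same rates) | 12.0% / 19.0% | 68.6% |
| 6% / 9.5% (half the rates, same relative effect) | 14.0% / 22.2% | 76.5% |
| 0% / 0% | 16.0% / 25.3% | 83.1% |
| 6% / 6% | 14.0% / 23.3% | 85.8% |
| 9% / 9% | 13.0% / 22.3% | 87.2% |

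**5. One-sided 0.05, 12% vs 19% among those kept:** 88.1% with 850 analysed, 78.8% with 637.5.

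**The case against.** - **The 25% refers to patients evaluated, is worded as a possibility, and sits in a paragraph about the recruitment pool.** This stands in part. Screening on age, BMI and chart data, and enrolment of some patients after the second evaluation day, could make the share among randomised patients much smaller. But the sentence removes patients from outcome analyses, and patients who were never enrolled would need no such removal.
- **The direction of the error is not shown.** This stands. If the rates come from all evaluated patients and those excluded respond little or not at all to the intervention, power among those kept can exceed 80%. A reader might infer that the trial is underpowered at 69%. The documents do not support that: it requires both that a full quarter of randomised patients is dropped and that 12% and 19% hold among the rest, and neither is stated.
- **A sharp cut-off would be over-precise.** This stands. The pooled formula leaves room to lose 12 of 850 (1.4%), but the unpooled and arcsine formulas leave 18 and 20, and 80% is itself rounded. Losses of about 5% or more are what matter.
- **The power paragraph does mention losses.** It cites little attrition, justified by medical record follow-up, and participation above 90%. Neither concerns transplant-ineligible patients, and neither enters as a reduction of the 850.
- **The test may be one-sided.** H1 is directional, but no text says the test is one-sided, and 850 is not the number that a one-sided calculation gives.

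**Conclusion.** The point holds as an unreconciled conflict between the Study Size Justification and the Power Calculation. On a two-sided 0.05 test, the printed 80% describes an analysis of essentially all 850 randomised patients, while the plan foresees leaving some patients out and adjusts nothing for it.

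If 12% and 19% apply to those kept, the chance of missing a 7-point effect rises from the stated 20% to about 24% with 10% left out and about 31% with 25% left out. If the rates apply to all evaluated patients and 25% are left out, power runs from about 69% to 87% under the assumptions shown. The missing items are the number analysed, the population behind the rates, and the sidedness. The conflict itself is well supported; no single replacement power figure is. It should be fixed.

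**What to change.** Reconcile the two paragraphs of C.4 by one of two routes.

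1. **Keep the exclusion.** State the sidedness, the number expected in the primary analysis, and the population to which 12% and 7 points apply. Restate the power or the detectable difference for that number. For example, if 25% of the 850 are excluded and 12% and 19% apply to those kept, with a two-sided 0.05 test: about 638 analysed, about 69% power for 7 points, or 80% power for 8.1 points. The sponsor should substitute its own expected share.
2. **Analyse all randomised patients**, as the wording of the primary outcome suggests. Remove the exclusion sentence, confirm that the rates apply to everyone randomised, and keep about 80%.

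The first route is a change of wording only, though the stated power may become less favourable. The second changes the primary analysis population and should be recorded as such. Neither needs extra patients.

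Separately, clarify what the 0.5 correlation means and how it was used. Each patient contributes one binary outcome, and the 80% is reproduced without it. That does not show what the sponsor actually computed, so the request is to explain the term, not to delete it.

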entered as covariates in subsequent analyses. We note that detected differences may be site-specific and will explore site stratifications if we observe differences. Multivariable modeling techniques will be employed, if necessary, to correct for lack of balance in demographic or clinical characteristics between the two groups. For the main outcome, we will use generalized linear mixed models (GLMMs) for adjusted analyses of the data, specifying the logit link function for the binary outcomes (i.e. at least one living donor inquiry over 12-month period). Treatment group will be the independent variable of primary interest, modeled as a fixed effect with the control group specified as reference group. We will also include fixed effects for any potential confounding covariates noted in bivariable analysis. A random intercept will be considered to increase generalizability of results. To control for potential contamination bias over the course of the study, we will consider controlling for time of study entry.

We will pursue a similar modeling technique as described above for secondary analyses except that change in each of the three dependent variables will be the continuous (vs. binary) outcomes. We will conduct exploratory analyses where we assess change in behavioral intentions and comfort in initiating conversations about LDKT as outcomes. All data will be analyzed by the program coordinator for the study at Emory University with the oversight of Drs. [name] and [name], who will be blinded to study allocation. SAS 9.3 (Cary, NC) will be used for all analyses.

C.5. Specific Aim 3: To conduct a process evaluation of the newly created web-based Living ACTS intervention by adapting commonly used process evaluation constructs (reach, recruitment, fidelity, dose delivered, dose received, and context) for an online environment In Table 3 we describe what data will be collected, how, and when. **Table 3.** Process evaluation components and measures (Linnan & Steckler, 2002)

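### The covariates and site term of the primary model are not fixed in advance, and the stated p<0.05 between-arm rule performs like no adjustment

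*Combined protocol and SAP*

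**What the plan says.** All of this is in the combined protocol and SAP, section C.4.

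**What is fixed.** The Statistical Analysis Plan sets a binary outcome, a generalised linear mixed model with logit link, arm as a fixed effect and control as the reference.

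**How covariates enter.**
- Baseline variables are compared between arms by t or chi-squared tests. "Variables found to have significant differences" at p<0.05 are "entered as covariates in subsequent analyses".
- "Multivariable modeling techniques will be employed, if necessary, to correct for lack of balance in demographic or clinical characteristics between the two groups". No threshold is attached.
- "We will also include fixed effects for any potential confounding covariates noted in bivariable analysis". The text does not say whether association with arm or with outcome is meant.

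**Site and time.**
- "A random intercept will be considered to increase generalizability of results". No grouping factor is named.
- On entry time, "we will consider controlling for time of study entry".
- On baseline differences that may be confined to one site, the team "will explore site stratifications if we observe differences".
- The Power Calculation is described as "accounting for potential correlation of patients within study sites".

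The Measurement paragraph points to Table 2 for covariates, but that table holds outcome measures only. Age, gender and education are listed as items collected, not as an adjustment set.

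**The concern.** Randomization in C.4 is simple 1:1, so any baseline difference between arms is due to chance. A significance test between arms then selects variables by chance, not by whether they predict inquiries. A strong predictor is left out about 95% of the time, and a useless variable is let in as often as a useful one.

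Beyond arm, the text does not settle which terms are in the primary model. Several models fit it, and they will not always fall on the same side of p<0.05. At stake are one identifiable test of H1 and a modest amount of precision from data the plan already collects.

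**Working it through.** **1. The plan's own figure.** Inputs from the Power Calculation and Study Size Justification: 12% against 19%, 850 patients at 1:1, alpha 0.05 (taken as two-sided).
- Mean rate: (0.12 + 0.19)/2 = 0.155.
- Null SE: √(2 × 0.155 × 0.845/425) = 0.02483.
- Alternative SE: √((0.12 × 0.88 + 0.19 × 0.81)/425) = 0.02471.
- Power: Φ((0.07 − 1.96 × 0.02483)/0.02471) = Φ(0.86) = 80.6%, against the stated 80%. The size needed is 419 per arm, 838 in all.

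The stated power follows from a plain two-proportion test with no site term or covariate. The sizing therefore does not tell us which model was intended.

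**2. The arm rule.** Each variable passes with probability 0.05. With k independent variables, the chance that at least one passes is 1 − 0.95^k: 14% for k = 3, 34% for k = 8, 64% for k = 20. The documents give no list, so k is an assumption.

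**3. Cost in power, by simulation.** Assumed, not in the documents:
- one baseline score with odds ratio (OR) 1.5 or 2.0 per SD for an inquiry;
- four equal sites with control rates 17/13/9/9% (mean 12%);
- no effect of entry time;
- fixed site terms standing in for a random intercept.

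True rates are 12% and 19%, with 20,000 trials per setting. N is 850, or 638 (850 × 0.75 = 637.5) if the roughly 25% exclusion in the Study Size Justification falls on randomised patients.

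| Power | N=850, OR 1.5 | N=850, OR 2.0 | N=638, OR 1.5 | N=638, OR 2.0 |
|---|---|---|---|---|
| Unadjusted | 0.802 | 0.805 | 0.684 | 0.684 |
| Arm rule | 0.802 | 0.808 | 0.685 | 0.686 |
| Arm rule plus outcome screening | 0.810 | 0.828 | 0.692 | 0.704 |
| Site and score fixed in advance | 0.817 | 0.834 | 0.699 | 0.713 |

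- Under the arm rule the score entered in 4.9% to 5.3% of trials, and power is within 0.3 points of no adjustment.
- Fixed model over arm rule: paired gain 1.4, 2.6, 1.5 and 2.7 points (SE 0.14 to 0.19).
- With outcome screening the score entered in 95% to 100% of trials, and the fixed model gains only 0.6 to 0.9 points. Adding site to an unadjusted model is itself worth 0.3 to 0.6 points.

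**4. Do the allowed versions agree?** With the same true effect:
- Arm rule only, site in or out, entry time in or out (four versions): verdicts on p<0.05 differ in about 3% to 5% of trials.
- With outcome screening also allowed (eight versions): 6.1%, 8.2%, 8.3% and 11.1% in the four settings; about 6% to 12% allowing for a repeat simulation.

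**5. Type I error.** Every single version gave 4.6% to 5.1% (SE 0.15).

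**6. The estimate.** The marginal odds ratio is (0.19/0.81)/(0.12/0.88) = 1.72. The fixed model averages 1.76 to 1.81 because it is conditional on covariates; that is not bias. The risk difference averages 0.070 in every model.

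**The case against.** **The two further sentences may add nothing.** The only bivariable tests described are those by arm, so both can fairly be read as restating the p<0.05 rule. That reading stands as possible, and for that reason 3% to 5% is reported beside 6% to 12%. A reader might infer that outcome screening is planned; the documents never describe it.

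**The choice need not follow the results.** The arm rule uses baseline data only and can be run before the 12-month inquiries arrive. The DSM Plan paragraph provides for early review and approval of the analysis plan, and the Blinding paragraph says analysts will not know the arm. These points stand and limit the concern. They do not name the model, and coded arms still show which version is significant.

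**Site may be intended.** The power statement mentions correlation within sites, so a site intercept is the natural reading, though it is unstated and optional. A reader might take the site-stratification sentence to decide whether site enters the primary model. It concerns site-specific baseline differences and does not support that.

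**The harm is small and assumed.** This is right for the power figures, which depend on an invented predictor and invented site rates. A weaker predictor gives less gain; with none, only the site part is left. The gap in the text does not depend on those inputs.

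**Conclusion.** The concern holds in a limited form. The arm rule is a poor way to choose covariates under randomisation, and the text leaves the covariates, the grouping factor and entry time unsettled. Under the assumptions shown, the cost is about 1 to 3 power points if only the arm rule operates and under 1 point if outcome screening was meant. The conclusion could turn on an unstated choice in about 3% to 5% of trials on the narrow reading, or 6% to 12% on the wide one.

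Three stronger conclusions are not supported:
- **That the plan inflates type I error.** No single version does, and an analysis without site is valid under simple randomisation. Reporting the most favourable of the eight versions would give 6.1% to 6.7%, but nothing in the documents says this will be done. Those figures are not a ceiling either: 16 versions under other assumed covariates gave 7.7%.
- **That the whole model is chosen after the data are seen.** Outcome, link, arm term and reference are fixed, and the arm rule is a stated algorithm.
- **That a particular baseline score is known to predict inquiries.** Interest in mediating pathways concerns change after the intervention, not baseline prognosis.

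Confidence is high on the gap in the text and lower on the size, which rests on assumed inputs.

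**What to change.** For the primary model, delete the p<0.05-by-arm rule, the bivariable-analysis route and the as-needed correction for imbalance. Before outcome data are seen, state one model: logistic regression with arm, site (three indicator terms) and a short named list of baseline variables already collected. The study team should choose the list on expected prognostic value. Make entry time a named sensitivity analysis. Report a standardised risk difference beside the odds ratio, because H1 and the power are stated as proportions.

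The cost is SAP wording. Expected inquiries are 425 × 0.12 + 425 × 0.19 = 132 at N=850, and 318.75 × (0.12 + 0.19) = 99 at N=638. With six terms (arm, three for site, two baseline variables) that is about 22 or 16 per term, which is workable. The downside is that the odds ratio becomes conditional on the covariates; the standardised risk difference keeps the result on the scale of the hypothesis.
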